9.3.2 Efficacy Analysis Populations

The analysis of primary efficacy endpoints is based on the intention-to-treat (ITT) population. All patients who enroll will be included, regardless of whether they receive consolidation Pembrolizumab. A secondary efficacy analysis will be conducted that excludes those patients who did not initiate consolidation Pembrolizumab after definitive therapy. At least 25 treatments of radiation should be delivered in order to be included in the analysis.

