3.1 General Design

This is a phase II, single arm, unblinded trial of about 12 months of consolidation Pembrolizumab after proton reirradiation with or without concurrent chemotherapy for isolated local and regional thoracic recurrences of NSCLC. Forty-one patients will be treated with re-irradiation with or without standard concurrent chemotherapy to all gross disease with proton beam therapy. The intended radiation dose should be at least 60 Gy of reirradiation in 1.8-2.0 Gy fractions with or without concurrent chemotherapy or in 4.0 Gy fractions without chemotherapy, at the provider's discretion. This corresponds to daily fractionated radiation over a period of approximately 3-8 weeks. Four to 12 weeks after completing reirradiation, patients will begin Pembrolizumab consolidation. Pembrolizumab will be given at a fixed dose of 200 mg intravenously approximately every 21 days for 17 cycles (about 12 months) if there is no evidence of progressive disease or intolerable side effects.

Subjects will be evaluated approximately 30 days prior to consolidation Pembrolizumab and every 12 weeks (1 day after until the day of the next infusion) while on Pembrolizumab with radiographic imaging to assess disease status. If new signs or symptoms of progression occur between scheduled scans, directed imaging will be obtained at the clinically appropriate time point to document disease status. Investigators will make all treatment-based decisions using RECIST 1.1. Adverse events will be monitored upon initiation of Pembrolizumab treatment and continue throughout the trial and graded in severity according to the National Cancer Institute (NCI) CTCAE version 5.0. For the

Phase II Pembrolizumab Reirradiation

Pembrolizumab phase, all treatment-related toxicities will be recorded.

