5.2 Treatment Regimen

Patients will be treated with reirradiation with or without standard concurrent chemotherapy to all gross disease with proton beam therapy. The intended radiation dose should be at least 60 Gy of reirradiation in 1.8-2.0 Gy fractions with or without concurrent chemotherapy or in 4.0 Gy fractions without chemotherapy, at the provider's discretion. This corresponds to daily fractionated radiation over a period of approximately 3-8 weeks. The decision to use concurrent chemotherapy, and which regimen to utilize, are left to the discretion of the treating oncologist. The chemotherapy regimen and doses will be recorded in the patient record.

Pembrolizumab will be started 4 to 12 weeks after completion of reirradiation. Pembrolizumab will be given at a dose of 200 mg intravenously approximately every 21 days for 17 cycles (about 12 months) if there is no evidence of progressive disease or intolerable side effects.

Dose Modifications (Escalation/Titration/Other)

Adverse events (both non-serious and serious) associated with pembrolizumab exposure may represent an immunologic etiology. These adverse events may occur shortly after the first dose or several months after the last dose of treatment. Pembrolizumab must be withheld for drug-related toxicities and severe or life-threatening AEs as per 3 below. See Section 5.6 for supportive care guidelines, including use of corticosteroids.

Table 1: Dose Modification Guidelines for Drug-Related Adverse Events

Toxicity	Hold Treatment For Grade	Timing for Restarting Treatment	Treatment Discontinuation
Diarrhea/Colitis	2-3	Toxicity resolves to Grade 0-1	Toxicity does not resolve within 12 weeks of last dose or inability to reduce corticosteroid to 10 mg or less of prednisone or equivalent per day within 12 weeks
	4	Permanently discontinue	Permanently discontinue
AST, ALT, or Increased Bilirubin	2	Toxicity resolves to Grade 0-1	Toxicity does not resolve within 12 weeks of last dose
	3-4	Permanently discontinue (see exception below) ^a	Permanently discontinue
Type 1 diabetes mellitus (if new onset) or Hyperglycemia	T1DM or 3-4	Hold pembrolizumab for new onset Type 1 diabetes mellitus or Grade 3-4 hyperglycemia associated with evidence of beta cell failure	Resume pembrolizumab when patients are clinically and metabolically stable

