8.1.5.3 Pre-Pembrolizumab Screening

Visit requirements are outlined in Section 7.0 - Trial Flow Chart.

Subjects will be eligible to move on to pembrolizumab treatment cycles if they received at least 50 Gy of reirradiation, if they have no progressive disease on tumor imaging, and if they do not have symptomatic CTCAEv5 grade ≥ 3 pneumonitis.

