9.3 Hypothesis/Evaluation

This phase II study evaluates a multi-stage treatment plan for recurrent disease that is comprised of definitive therapy consisting of proton reirradiation with or without chemotherapy, followed by consolidation Pembrolizumab, for recurrent NSCLC. A total of 41 patients will be enrolled on the study. Between the end of definitive therapy and the start of Pembrolizumab, there is a 4-12 week rest period. The primary intent-to-treat analysis will estimate PFS from start of definitive therapy, regardless of whether consolidation Pembrolizumab was administered. A secondary proof of principle analysis will estimate PFS in the subgroup of patients who receive definitive therapy followed by consolidation Pembrolizumab. The benefit of adding Pembrolizumab after definitive therapy will be determined in this analysis, by testing whether PFS is improved as compared to a historical control population who received standard therapy only. For this proof of principle analysis, the null hypothesis is that the median PFS from start of therapy for a recurrence of NSCLC is 6 months as compared to the alternative hypothesis that the median PFS is increased to 10 months.

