9.4 Statistical Methods

Primary Objective

1. The primary intent-to-treat analysis will estimate progression free survival from initiation of definitive therapy by the Kaplan-Meier method. Median PFS and 95% CI will be determined. A total of 41 patients will be enrolled on the study.
2. A secondary proof of principle analysis will determine the clinical benefit of adding consolidation Pembrolizumab after definitive therapy. Only patients who receive consolidation Pembrolizumab are included in this analysis. It is expected that up to 15% of enrolled patients will have progressive disease or lingering toxicity and will not start Pembrolizumab after definitive therapy. Thus we anticipate that at least 35 patients will be included.

In this proof of principle analysis, we will compare progression free survival from initiation of definitive therapy to a historical control value. We assume the median PFS for the historical control population treated with standard therapy only is 6 months and the median PFS for the patients treated with definitive therapy and consolidation Pembrolizumab is 10 months. Assuming 35 patients are enrolled over 2 years and followed for an additional 3 months, the final analysis will have 80% power to detect an improvement in median PFS assuming exponential survival and 1-sided 5% significance level.

Secondary Objectives

1. Overall survival will be estimated by the Kaplan-Meier method. Median OS and 95% CI will be determined.
2. Toxicities will be graded, categorized and tabled. For the definitive therapy phase, we will report on adverse events which are grade 3 or higher treatment-related toxicities or any grade of pneumonitis or esophagitis. For the Pembrolizumab phase, we will report all treatment-related toxicities.

Exploratory Objective

1. Biomarkers will be tested for association with PFS using log rank test for categorical biomarkers and Cox proportional hazards regression for continuous biomarkers. Biomarkers will be tested for association with graded toxicity (i.e., worse toxicity grade) for specific categories of toxicity using chi square test for categorical biomarkers and Spearman's correlation for continuous biomarkers.

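### The 25-treatment rule in section 9.3.2 excludes patients who complete the permitted 4.0 Gy schedule, although section 9.4 defines the tested set by pembrolizumab receipt alone

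*Combined protocol and SAP*

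**What the plan says.** Section 9.3.2 describes two efficacy sets. The primary intention-to-treat set takes every enrolled patient, whether or not pembrolizumab follows. The secondary set leaves out patients who did not start pembrolizumab. The section then closes with "At least 25 treatments of radiation should be delivered in order to be included in the analysis", without saying which analysis is meant and without an exception by fraction size.

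The other definitions of the secondary, proof-of-principle set contain no treatment count. Section 9.3 estimates PFS "in the subgroup of patients who receive definitive therapy followed by consolidation Pembrolizumab". Section 9.4 says: "Only patients who receive consolidation Pembrolizumab are included in this analysis". Its size is derived from an expectation that "up to 15% of enrolled patients will have progressive disease or lingering toxicity and will not start Pembrolizumab", followed by "Thus we anticipate that at least 35 patients will be included".

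On treatment, section 5.2 (and section 3.1 in the same terms) gives the intended dose as "at least 60 Gy of reirradiation in 1.8-2.0 Gy fractions with or without concurrent chemotherapy or in 4.0 Gy fractions without chemotherapy", with the choice left to the treating provider. Both sections then state the duration: "This corresponds to daily fractionated radiation over a period of approximately 3-8 weeks". Section 8.1.5.3 lets patients go on to pembrolizumab if, among other conditions, "they received at least 50 Gy of reirradiation". That is a dose, not a number of treatments. Sections 5.9 and 9.2 count anyone with one dose of proton reirradiation as evaluable.

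**The concern.** A rule stated as a number of treatments means different things at different fraction sizes. Twenty-five treatments lie below a 60 Gy course at 1.8 to 2.0 Gy per fraction but well above one at 4.0 Gy. Read literally, section 9.3.2 removes patients who received the whole regimen as the protocol permits it, while section 9.4 keeps them.

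The primary analysis only estimates a Kaplan-Meier median with its confidence interval. The comparison with the 6-month historical median, and the power statement, belong to the proof-of-principle set. If anyone is treated at 4.0 Gy, an analyst following section 9.3.2 and one following section 9.4 would run that test on different patients.

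The difference is not random. The 4.0 Gy option is limited to patients without chemotherapy and chosen by the provider, so the reduced set would no longer represent the regimen under study. In an open-label, single-arm trial, leaving the choice between the two definitions open also means it could be made after outcomes are known.

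**Working it through.** **Treatments per course** (dose divided by fraction size; sections 5.2, 8.1.5.3 and 9.3.2)

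| Fraction size | 60 Gy course | 50 Gy check | Dose at 25 treatments |
|---|---|---|---|
| 2.0 Gy | 60/2.0 = 30 | 50/2.0 = 25 | 50 Gy |
| 1.8 Gy | 60/1.8 = 33.3, so 34 | 50/1.8 = 27.8, so 28 | 45 Gy |
| 4.0 Gy | 60/4.0 = 15 | 50/4.0 = 12.5, so 13 | 100 Gy |

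At five treatments a week (an assumption), 15 treatments take three weeks, the short end of the stated 3 to 8 weeks. Anyone on 1.8 or 2.0 Gy who passes the 50 Gy check already has at least 25 treatments. Among patients who pass the check, then, the count removes only those on 4.0 Gy.

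**Planned size of the tested set.** 41 × 0.85 = 34.85, which gives the plan's 35. The 15% covers only progression or lingering toxicity before pembrolizumab.

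**Reproducing the stated 80% power.** Inputs from section 9.4: n = 35, accrual A = 24 months, further follow-up F = 3 months, medians 6 and 10 months, exponential PFS, one-sided 5%. With λ = ln 2/median and uniform accrual, the probability of an event is

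1 − [exp(−λF) − exp(−λ(A+F))]/(λA).

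- Median 6: λ = 0.1155, probability 0.761, expected events d0 = 35 × 0.761 = 26.6.
- Median 10: λ = 0.0693, probability 0.604, expected events d1 = 35 × 0.604 = 21.1.

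For a test on the log hazard, with the null variance for the critical value and the alternative variance for power:

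Φ{[ln(10/6) − 1.645/√26.63] × √21.15} = Φ{(0.511 − 0.319) × 4.599} = Φ(0.883) = 81.1%.

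This agrees with the plan's 80%.

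**Effect of removing the 4.0 Gy patients.** The documents do not give the share on 4.0 Gy, so the shares below are assumptions. Section 9.4 does not name the test, so three versions are shown: the formula above, and a one-sample log-rank test simulated with 200,000 replicates per cell under two variance choices (E is the expected and O the observed number of events). The formula uses fractional n (31.5, 24.5, 17.5). The simulations use the whole numbers shown.

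| Share on 4.0 Gy | n | Formula | Log-rank, variance E | Log-rank, variance (O+E)/2 |
|---|---|---|---|---|
| 0% | 35 | 81.1% | 78.1% | 81.5% |
| 10% | 32 | 77.7% | 74.5% | 78.4% |
| 20% | 28 | 73.7% | 69.4% | 73.8% |
| 30% | 24 | 69.1% | 63.2% | 68.5% |
| 50% | 18 | 57.7% | 51.9% | 58.5% |

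Simulated size is 3.6 to 3.9% with variance E and 5.1 to 5.3% with (O+E)/2. The loss against n = 35, across the three columns, is about 3 to 4 points at 10%, 7 to 9 at 20%, 12 to 15 at 30% and 23 to 26 at 50%. Rounding 24.5 up to 25 instead of down gives 64.6% and 69.7% in the 30% row, so those losses are slightly overstated.

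**The case against.** The strongest objection is that the practical effect is unknown. Fractionation is left to the provider, and if no one receives 4.0 Gy the tested set does not change. That stands: the power figures are illustrations and should not set the weight of the point. The contradiction in the text remains whatever the share.

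Second, the sentence most naturally attaches to the secondary analysis just before it, which leaves the primary estimate untouched. That also stands. Only if the sentence covers the primary analysis does it contradict the inclusion of all enrolled patients and the one-dose evaluability rule in sections 5.9 and 9.2. It would then also drop patients who stop radiation early for progression, toxicity or death, which by itself tends to lengthen PFS. The net direction is not established, because the 4.0 Gy patients would go too and their PFS is unknown. The 4.0 Gy patients are excluded on either reading.

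Third, 15% is a ceiling. With fewer losses, some exclusions could occur before the set falls below 35: up to 41 − 35 = 6 losses and exclusions together. This softens the power argument but not the conflict over who is analysed.

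Fourth, the count could also remove someone who started pembrolizumab by deviation after less than 50 Gy. That is true, but outside the protocol's own pathway.

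Finally, the rule is worded as a recommendation. It is nevertheless phrased as a condition of inclusion, and treating it as optional would leave the set undefined.

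**Conclusion.** The point holds. A completed 60 Gy course in 4.0 Gy fractions is 15 treatments and cannot meet a 25-treatment condition. No section exempts these patients, and sections 9.3 and 9.4 define the tested set without the condition. As written, the plan gives two populations for its only hypothesis test, and this needs correcting before analysis.

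The contradiction needs no assumption beyond the plan's own dose and fraction sizes. The power loss rests on an assumed 4.0 Gy share, the full 15% loss before pembrolizumab, exponential PFS and the choice of test. It ranges from none at a 0% share to 23 to 26 points at 50%. The seriousness comes from the undefined and selectively reduced test population, not from those figures.

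**What to change.** Delete the treatment count from section 9.3.2 as a condition for the efficacy analyses. The primary set then remains all enrolled patients, as that section already says, and the secondary set is the patients who receive consolidation pembrolizumab, as section 9.4 says. Possible wording: *No minimum number of radiation treatments applies to the primary or secondary efficacy analysis.*

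If the sponsor wants a radiation-delivery criterion, it should be a labelled sensitivity analysis, fixed before the data are examined and defined so that a completed course on any permitted schedule satisfies it. In the same edit, sections 3.1, 5.2, 5.9, 8.1.5.3, 9.2, 9.3.2 and 9.4 should be reconciled, including how all enrolled patients relate to the 41 evaluable patients with at least one dose. This takes no position on which dose, schedule or threshold is right.

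The cost is one sentence, plus one line if a sensitivity analysis is added. No patients or data are lost.

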9.3.3 Safety Analysis Populations

The All Patients as Treated (APaT) population will be used for the analysis of safety data in this study. The APaT population consists of all enrolled subjects who received at least one dose of study treatment. At least one laboratory or vital sign measurement obtained subsequent to at least one dose of trial treatment is required for

inclusion in the analysis of each specific parameter. To assess change from baseline, a baseline measurement is also required.

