9.2 Sample Size Determination

The sample size will be 41 evaluable patients; i.e.: subjects who receive at least 1 dose of proton reirradiation.

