9.3.1 Analysis Endpoints

Primary

Progression Free Survival (PFS) per RECIST 1.1

Progression Free Survival is defined as the time from initiation of definitive therapy to the first documented disease progression per RECIST 1.1 based on radiologists' review or death due to any cause, whichever occurs first, or last patient follow-up that documented lack of disease progression. Patients who have not had disease progression or who have died, will be censored on the most recent clinical evaluation date that documented that they were progression-free.

Secondary

Overall Survival

Overall Survival (OS) is defined as the time from initiation of definitive therapy to death due to any cause or last patient contact alive. Subjects without documented death at the time of the final analysis will be censored at the date of the last follow-up.

Toxicity Determination

Tolerability of therapy will be determined on the basis of CTCAE adverse event reporting. Toxicity will be reported separately for definitive therapy and Pembrolizumab. For the definitive therapy phase, we will report on adverse events which are grade 3 or higher treatment-related toxicities or any grade of pneumonitis or esophagitis. For the Pembrolizumab phase, we will report all treatment-related toxicities.

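### One safety population, with study treatment undefined, is set for two phase-specific toxicity reports whose exposed groups may differ by about 6 of 41 patients

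*Combined protocol and SAP*

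**What the plan says.** Section 9.3.3 names one population for safety: "The All Patients as Treated (APaT) population will be used for the analysis of safety data in this study". Its entry rule is: "The APaT population consists of all enrolled subjects who received at least one dose of study treatment". The term *study treatment* is not defined there, and the next sentence of the section changes to *trial treatment*.

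Section 9.3.1 splits the reporting: "Toxicity will be reported separately for definitive therapy and Pembrolizumab". For definitive therapy, "we will report on adverse events which are grade 3 or higher treatment-related toxicities or any grade of pneumonitis or esophagitis". Section 9.4 repeats that rule and adds: "For the Pembrolizumab phase, we will report all treatment-related toxicities". Neither section names a population for either report.

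The plan expects the two exposed groups to differ. Section 9.2 counts as evaluable the "subjects who receive at least 1 dose of proton reirradiation", 41 in all. Section 9.4 expects up to 15% of enrolled patients who "will have progressive disease or lingering toxicity and will not start Pembrolizumab after definitive therapy", leaving at least 35. Section 8.1.5.3 also bars patients with symptomatic pneumonitis of grade 3 or higher from the pembrolizumab cycles.

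**The concern.** The two toxicity reports describe two exposures, and the groups exposed are not the same. A single set defined by one dose of an undefined treatment cannot be the correct denominator for both, unless it is applied separately within each phase.

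The documents give support for two meanings of the term:

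- **Pembrolizumab only.** The Study Summary names pembrolizumab as the study product. Table 6 (section 7.1) marks administration of trial treatment only at the pembrolizumab cycles. Section 8.1.5.1 ties the first dose of trial treatment to pembrolizumab.
- **Reirradiation included.** Sections 5.9 and 9.2 base evaluability on one dose of proton reirradiation. Section 9.3 says the study evaluates a multi-stage plan of which reirradiation is a part.

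The first meaning is the more troublesome. It removes irradiated patients from the reirradiation report, and it removes some of them because they had toxicity. Pneumonitis is both a bar to pembrolizumab (8.1.5.3) and an event that the definitive-therapy report must capture (9.3.1). The second meaning puts patients who never received pembrolizumab into its denominator, where they cannot contribute an event caused by it. Toxicity is a stated secondary objective, and a single-arm trial has no internal comparator against which a shifted rate would show up.

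**Working it through.** **Inputs from the documents.** 41 patients (9.2); up to 15% not starting pembrolizumab, hence at least 35 starters (9.4). The documents give no toxicity event counts, so every count below is an assumption.

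**The plan's own figure.** 41 × (1 − 0.15) = 34.85, which rounds to 35. The stated figure is reproduced. Non-starters: 41 × 0.15 = 6.15, about 6.

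**If study treatment includes reirradiation.** The set has 41 patients, of whom about 35 received pembrolizumab. Every pembrolizumab rate is multiplied by 35/41 = 0.854, a relative understatement of 1 − 0.854 = 14.6%. With 7 events assumed:

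- correct: 7/35 = 20.0% (exact 95% CI 8.4% to 36.9%)
- reported: 7/41 = 17.1% (7.2% to 32.1%)

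**If study treatment means pembrolizumab.** The set has about 35 patients, and the definitive-therapy report loses about 6 irradiated patients together with their events. Assume 4 of the 35 starters had a reportable event, so the report shows 4/35 = 11.4%. The rate among all irradiated patients depends on how many of the 6 non-starters had an event:

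| Non-starters with an event | Rate among all irradiated | Reported |
|---|---|---|
| 0 of 6 | 4/41 = 9.8% | 11.4% |
| 1 of 6 | 5/41 = 12.2% | 11.4% |
| 3 of 6 | 7/41 = 17.1% | 11.4% |
| 6 of 6 | 10/41 = 24.4% | 11.4% |

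The reported rate is too low whenever the event rate in non-starters exceeds that in starters. In this example one affected non-starter is enough. The toxicity-related reasons for not starting in 8.1.5.3 and 9.4 make that likely. It is not certain, because 9.4 does not say how the non-starters divide between progression and toxicity.

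**Are the events recorded at all?** Sections 3.1, 8.1.2.1 and 8.2 start adverse event recording with pembrolizumab, and Table 6 shows no adverse event review in the reirradiation column. A patient who never reaches cycle 1 has no scheduled recording. Take the third row of the table. If the 6 non-starters were added to the denominator but their 3 events were never recorded, the report would show 4/41 = 9.8% where the true rate is 17.1%. That is further from the truth than the 11.4% from starters alone. The denominator and the recording rule therefore have to be corrected together.

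**The case against.** The strongest reply is that an all-patients-as-treated population is naturally applied phase by phase. Section 9.3.1 asks for separate reports, and both 9.3.1 and 9.4 specify their content by phase. A patient who never received pembrolizumab was never in that phase. On that reading both denominators are right. Section 9.4 also promises only that toxicities will be graded, categorized and tabled; it prescribes no rate. And 9.3.2 shows that the authors separate starters from non-starters when they analyse efficacy.

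Much of this stands. A reader might infer that every reading of 9.3.3 gives one report a wrong denominator; the phase-by-phase reading shows that this goes too far. But the separation in 9.3.1 concerns reporting, while 9.3.3 gives a single rule for all safety data. A prespecified denominator should not rest on an unstated inference. The care taken in 9.3.2 also makes the silence in 9.3.3 look like an omission.

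The sizes are modest too. The 15% is the plan's expected maximum, and the 2.9-point shift in the pembrolizumab example (20.0% to 17.1%) is small beside an interval of 8.4% to 36.9%. A table that printed counts beside the number of starters would let readers correct it. That answers the dilution. It does not answer the loss of irradiated patients, whose events would not appear in the table at all.

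**Conclusion.** The point holds as a missing definition with a practical consequence. Section 9.3.3 gives one population and an undefined term for two reports whose exposed groups are expected to differ by up to about 6 of 41. Unless an analyst supplies the phase-by-phase rule, one report has the wrong denominator.

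- With reirradiation included, pembrolizumab rates are multiplied by as little as 0.854. This rests only on the plan's 41 and 15%; fewer non-starters means less dilution.
- With pembrolizumab only, the definitive-therapy rate is likely understated. The example of 11.4% against 9.8% to 24.4% rests on assumed counts.

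Two stronger conclusions might be drawn, and the documents support neither. One is that the reirradiation rate is certainly biased downward: if no non-starter has an event, the starters-only figure is too high. The other is that this is the trial's only formal safety output. Section 3.1 also lists time to first grade 3 to 5 event and prespecified events of clinical interest, and 3.4 sets safety endpoints of its own. Those analyses would use the same undefined population.

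The primary endpoint is not affected. The change should be made, but the trial's main conclusion does not depend on it.

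**What to change.** In 9.3.3, replace the single rule with two sets:

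- a reirradiation safety set: all patients who received at least one proton fraction;
- a pembrolizumab safety set: all patients who received at least one pembrolizumab dose.

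Use each as the denominator of its own toxicity table. In the reirradiation table, show the patients who did not go on to pembrolizumab separately, with the reason. Define *study treatment* and *trial treatment* once and use them consistently.

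In the same amendment, reconcile 3.1, 8.1.2.1, 8.2 and Table 6, which start adverse event recording or review at pembrolizumab cycle 1, with 9.3.1 and 9.4, which promise a definitive-therapy report. The events listed for that phase need to be recorded for everyone irradiated, including non-starters. The pembrolizumab set works without this step; the reirradiation set does not.

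The cost is a few sentences in 9.3.3 and the adverse event sections, and recording of the already promised events at the reirradiation visits that Table 6 already contains. No extra patients are needed. The reirradiation toxicity rate may come out less favourable.
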